## LIST OF ABBREVIATIONS

AE	adverse event
BMI	body mass index
bpm	beats per minute
CMH	Cochran-Mantel-Haenszel
CRF	case report form
CSR	clinical study report
C-SSRS	Columbia-Suicide Severity Rating Scale
ECG	electrocardiogram
FAS	full analysis set
GEE	generalized estimating equation
IWRS	interactive web response system
LOCF	last observation carried forward
MedDRA	Medical Dictionary for Regulatory Activities
NSAIDs	nonsteroidal anti-inflammatory drugs
OLE	open label safety extension
PedMIDAS	pediatric migraine disability assessment
QTc	corrected QT
QTcB	Bazett's corrected QT
QTcF	Fridericia's corrected QT
SAE	serious adverse event
SAP	statistical analysis plan
SD	standard deviation
TEAE	treatment-emergent adverse event
TLFs	tables, listings, figures
WHO	World Health Organization
ZNS	zolmitriptan nasal spray

## 1. INTRODUCTION

This statistical analysis plan (SAP) describes the statistical analysis methods and data presentations to be used in tables, listings, and figures (TLFs) in the clinical study report (CSR) for Study IPX229-B16-01. This SAP is based on the study protocol amendment 3 dated 13Dec2017.

### 1.1. Study Designs and Objectives

The primary objective of the study is to evaluate the efficacy and safety of zolmitriptan nasal spray (ZNS) in the acute treatment of migraine headache in subjects ages 6 to 11 years.

This is a randomized, double-blind, placebo-controlled, 2-period, crossover outpatient study (See [Figure 1](#)). Within 2 weeks of screening, eligible subjects will return to the study site to begin a 6-week single-blind run-in period, during which a single migraine headache will be treated with 1 dose of placebo. Subjects will be instructed to treat a headache of moderate or severe pain intensity within approximately 20 minutes of onset of headache pain reaching moderate or severe intensity and to complete a diary capturing the headache severity using a 4-point headache pain intensity scale (severe = 3, moderate = 2, mild = 1 or none = 0), other associated symptoms, and use of rescue medication(s). Headaches occurring while the child is at school will not be treated with study drug. Adverse events (AEs) will also be collected. Diary entries are to be recorded immediately prior to treatment with study drug and after treatment at 30 minutes, 1 and 2 hours. If, after 2 hours, the migraine headache has not responded (ie, reduced to a pain intensity of mild or none), the subject is permitted to use protocol-allowed rescue medication(s). Any subsequent migraine episodes during the run-in period will be treated with the subject's protocol-allowed pre-study acute migraine medication. Subjects who have not treated a migraine headache with blinded placebo during the 6-week run-in period will be considered screen failures. Placebo challenge responders (defined as those subjects who treat a migraine attack of moderate (2) or severe (3) intensity and who achieve a mild (1) or none (0) response within 2 hours after dosing) will be discontinued from the study.

[figure not shown]
Eligible placebo non-responders will be randomized to one of two treatment sequences within their respective body weight stratum determined immediately prior to randomization: ZNS followed by placebo or placebo followed by ZNS ([Table 1](#)). Subjects weighing less than 50 kg will be allocated randomly to receive ZNS 2.5 mg or 1 mg in a 5:1 fashion during the ZNS treatment. Subjects weighing at least 50 kg will be allocated randomly to receive ZNS 5 mg or 2.5 mg in a 5:1 fashion during the ZNS treatment ([Table 2](#)). Following randomization, subjects will have up to 6 weeks to treat a migraine attack of moderate or severe intensity. During each treatment period, subjects will treat a single moderate to severe migraine attack with study drug within approximately 20 minutes of the headache pain reaching moderate or severe intensity. Headaches occurring while the child is at school will not be treated with study drug. Headache pain intensity will be assessed by the subjects immediately prior to treatment with study drug and at 30 minutes, 1, 2, and 24 hours postdose using a subject diary containing the 4-point headache pain intensity scale. Associated migraine symptoms will also be assessed at these time points. Subjects who do not obtain satisfactory relief of migraine pain by 2 hours after taking study drug will be permitted to treat with their protocol-allowed pre-study acute migraine medication (eg,

nonsteroidal anti-inflammatory drugs [NSAIDs] or acetaminophen) at that time or at any time thereafter, if the headache does not resolve or if it recurs, with the exception that all triptans and ergot derivatives are prohibited for 24 hours following the dose of study treatment. After treating a migraine attack in the first treatment period, the subject will return to the study site to receive study drug for the second treatment period. Subjects will then have up to 6 weeks to treat a second migraine attack of moderate or severe intensity.

Subjects who successfully complete the double-blind portion of this study and continue to be eligible will be offered participation in a 6-month outpatient open-label safety extension (OLE; Part 2) where they will treat up to 4 moderate to severe migraine attacks per month with ZNS. The occurrence, continuance, or recurrence of migraine headache pain for up to 72 hours after the onset of a migraine attack is considered to be part of this attack and is not considered a separate attack, regardless of treatment. Headaches occurring while the child is at school will not be treated with study drug. During the OLE, subjects will assess their pain-free status immediately prior to treatment with ZNS and 2 hours after the first dose for each migraine attack treated with ZNS. Subjects who do not obtain satisfactory relief of migraine pain by 2 hours after taking study drug, or if the headache recurs after 2 hours, are permitted to treat with a second dose of their study drug and/or their protocol-allowed pre-study acute migraine medication (eg, NSAIDs or acetaminophen). For each migraine attack, diary entries will only be made for the first dose of study drug; a second dose of study drug may not be administered within 2 hours of the first dose and no more than 2 doses of study drug are permitted within a 24-hour period and for any single attack. Other triptans and ergot derivatives are prohibited for 24 hours following the last dose of study drug treatment. Migraine-associated disability, using the PedMIDAS questionnaire, will be assessed at the end of study.

**Figure 1: Study Flow Chart**

**Table 1: Randomization Schedule for Study IPX229-B16-01**

	Treatment Period 1	Treatment Period 2
Sequence 1	ZNS	ZNS Placebo
Sequence 2	ZNS Placebo	ZNS

Subjects weighing less than 50 kg will be allocated randomly to receive ZNS 2.5 mg or 1 mg in a 5:1 fashion during the ZNS treatment. Subjects weighing at least 50 kg will be allocated randomly to receive ZNS 5 mg or 2.5 mg in a 5:1 fashion during the ZNS treatment. The two dose levels are described in [Table 2](#).

**Table 2: Dose Levels during Double-Blind Treatment Period**

Weight (kg)	Dose Level (Number Randomized)	
	Low (n=48)	High (n=240)
<50	1 mg	2.5 mg
≥50	2.5 mg	5 mg

During the OLE, all eligible subjects will receive ZNS. Subjects weighing <50 kg will receive 2.5 mg and those weighing at least 50 kg will receive 5 mg, with the option to reduce to 2.5 mg if tolerability is an issue.

## 1.2. Sample Size and Power

Part I of this study is a randomized, double-blind, placebo-controlled, 2-period, crossover outpatient study with a 6-week placebo run-in period.

Approximately 426 subjects will be enrolled to the placebo run-in period to randomize 288. With the 5:1 (high dose:low dose) randomization ratio for each of the two weight strata, it is estimated that 240 subjects will be randomized in the high-dose group and 48 subjects will be randomized to the lower dose level.

The sample size is based on detecting a difference in the percentage of subjects treated with a high dose (2.5 mg in the <50 kg weight stratum and 5 mg in the ≥50 kg weight stratum) who are pain free at 2 hours between ZNS and placebo. In this crossover trial, 240 high-dose-treated subjects will be adequate to detect a clinically relevant difference of 0.11 in the percentage of subjects who are pain free at 2 hours between ZNS and placebo as statistically significant (0.05, two tailed) with 90% power assuming a standard deviation of 0.5.

Approximately 48 subjects will be randomized in the low dose level (1 mg in the <50 kg weight stratum and 2.5 mg in the ≥50 kg weight stratum). The data from the low dose level will be summarized to explore dose-response relationship.

Based on other migraine crossover studies, dropout rates during the placebo run-in period ranged from 12% to 50%. Based on this, approximately 426 subjects will be enrolled into the placebo run-in period to randomize 288. This allows for approximately 32% dropout during placebo run-in period.

Approximately 100 subjects who complete the double-blind crossover phase will enter the 6-month OLE to enable at least 50 subjects to complete at least 6 months treating on average at least one migraine attack per month (treating up to 4 migraine attacks per month) with ZNS. Part II of the study is an OLE with subjects who successfully complete Part I of the study.

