## **2. GENERAL CONSIDERATIONS FOR DATA ANALYSIS**

Part 1 and 2 of the study will be analyzed separately. Separate sets of tables, listings and figures will be prepared for Part 1 and Part 2.

After all subjects have completed the double-blind phase of the study (Part I) or prematurely discontinued from the study, all data in Part I will be cleaned, the database will be frozen (soft lock), the study will be unblinded, and an analysis of Part I (double-blind) data will be performed. This will be the primary analysis of the study and a type I error rate (5%) will be allocated for this analysis.

All statistical tests will be 2-sided and performed at the 5% significance level, without multiplicity adjustment.

Likewise, after all subjects have completed Part II (OLE) of the study or prematurely discontinued from the study, all outstanding data queries have been resolved or adjudicated as unresolvable, and the data have been cleaned and finalized, the final analysis of the data will be performed. This final analysis will mainly focus on the OLE.

Analysis results will be presented using descriptive statistics. For categorical variables, the number and percentage of subjects in each category will be presented; for continuous variables, descriptive statistics (the number of subjects [n], mean, standard deviation [SD], median, minimum, and maximum) will be presented.

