### **2.1.2. Full Analysis Set**

The full analysis set (FAS) includes all subjects who were randomized and administered at least one dose of post randomization study drug. The analysis of all efficacy variables will be performed using the FAS and will be analyzed separately for high dose and low dose groups.

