- Time to rescue medication. For those subjects who did not use rescue medication, the time to rescue medication is censored at 24 hours after dosing. Additionally, descriptive summary of time to rescue medication will be presented for those subjects who did take a rescue medication. Note: if subject diary includes records of rescue medication that started prior to the start of migraine, such medications will be ignored as incorrect diary entry. If rescue medications are recorded with missing start date/time, time to rescue medication will be imputed as zero.

For all proportion endpoints, a GEE model similar to the primary analysis will be conducted for the low dose group and high dose group separately.

For the time to use of rescue medication, a Cox proportional hazards model for crossover data ([France et al 1991](#)) with treatment, period, weight, and baseline headache pain intensity will be used.

Time to use of rescue medication will also be presented graphically using the Kaplan-Meier estimates.

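### The low-dose arm is there to explore dose response, but modelling the doses separately plans no high-versus-low estimate and leaves between-child placebo information unused

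*SAP*

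**What the plan says.** - **Purpose of the arm.** SAP section 1.2 expects that "240 subjects will be randomized in the high-dose group and 48 subjects will be randomized to the lower dose level", and of the smaller group says "The data from the low dose level will be summarized to explore dose-response relationship".
- **Analysis sets.** Section 2.1.2 says efficacy variables "will be analyzed separately for high dose and low dose groups".
- **Models.** The primary GEE in section 5.1 takes high-dose children only. Section 5.3 lists low-dose 2-hour pain freedom as a secondary endpoint and says of all proportion endpoints that "a GEE model similar to the primary analysis will be conducted for the low dose group and high dose group separately". The code in section 8.1 has treatment, period, a two-level sequence, weight category and predose severity, and no dose term.
- **Testing rule.** Section 2: "All statistical tests will be 2-sided and performed at the 5% significance level, without multiplicity adjustment".
- **Descriptive output.** Section 2.2 provides summaries by weight group and dose.
- **Design.** Section 1.2 describes the dose allocation: "With the 5:1 (high dose:low dose) randomization ratio for each of the two weight strata". Section 2.3 assigns sequence 1:1 within each dose group, so every child is scheduled for one placebo period.

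No model, test or interval in the SAP compares the high dose with the low dose.

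**The concern.** A dose-response question asks how far the two doses differ. The plan produces two separate comparisons with placebo and leaves the reader to set them side by side. One being significant and the other not is no evidence of a dose difference, above all when one rests on 240 children and the other on 48.

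The low-dose model also sees only low-dose children. Dose is randomized within weight stratum and both dose groups have a placebo period, so the high-dose children's placebo attacks estimate the same placebo rate. They could sharpen both the low-versus-placebo and the high-versus-low estimates. What is at stake is the precision and usefulness of an exploratory result for which 48 children are randomized.

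**Working it through.** **Inputs from the SAP.** Section 1.2 states that "240 high-dose-treated subjects will be adequate to detect a clinically relevant difference of 0.11" "with 90% power assuming a standard deviation of 0.5". Alpha is 0.05 two-sided; group sizes are 240 and 48.

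**Assumptions.** SD 0.5 is read as the SD of the within-child difference. The within-child correlation ρ is not in the SAP and is taken as 0 to 0.5. With per-attack variance s² = 0.5²/[2(1−ρ)], and s² at most 0.25 for a yes/no outcome, ρ cannot exceed 0.5. All 48 and 240 children are taken to contribute both attacks.

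**The plan's own figures.** The split is exact: 288 × 5/6 = 240 and 288/6 = 48. The paired normal formula gives n = [(1.960 + 1.282) × 0.5/0.11]² = 217.1, so 218. At 240 the power is 92.6%, so 240 is adequate for the stated 90%. A parallel-group reading of the same SD would need 435 per arm, so the within-child reading is the one that fits.

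**Low dose as planned (48 alone).** SE = 0.5/√48 = 0.0722. Power for 0.11 = Φ(0.11/0.0722 − 1.96) = 33%. The 95% CI half-width is 0.141, and the difference detectable with 80% power is 2.80 × 0.0722 = 0.202.

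**High minus low by subtracting the separate estimates.** SE = 0.5 × √(1/48 + 1/240) = 0.0791; detectable difference at 80% power 0.221.

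**One joint model (placebo, low, high; two-level sequence).**
- Var(low − placebo) = s²[(1−ρ²)/48 + (1−ρ)²/288]
- Var(high − low) = s²(1−ρ²)(1/48 + 1/240)

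Example at ρ = 0: s² = 0.125. Var(low − placebo) = 0.125 × (1/48 + 1/288) = 0.003038, SE 0.0551. Var(high − low) = 0.125 × 0.025 = 0.003125, SE 0.0559.

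| ρ | s² | SE low − placebo | cut | power for 0.11 | SE high − low | 80%-power detectable high − low |
|---|---|---|---|---|---|---|
| separate models | – | 0.0722 | – | 33% | 0.0791 | 0.221 |
| 0 | 0.125 | 0.0551 | 24% | 51% | 0.0559 | 0.157 |
| 0.2 | 0.156 | 0.0589 | 18% | 46% | 0.0612 | 0.172 |
| 0.3 | 0.179 | 0.0607 | 16% | 44% | 0.0637 | 0.179 |
| 0.5 | 0.250 | 0.0642 | 11% | 40% | 0.0685 | 0.192 |

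Put another way, the 48 children carry the information of about 82 (ρ = 0) down to 61 (ρ = 0.5).

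**Check on the logit scale.** Separate and joint GEEs were simulated with 48 + 240 children, assumed pain-free rates of 20% (placebo), 26% (low) and 31% (high), and 300 runs for each of three latent correlations (0, 0.35, 0.6). The SD of the low-dose log odds ratio fell from 0.599 to 0.381, from 0.481 to 0.365 and from 0.440 to 0.344, cuts of 36%, 24% and 22%. The direction agrees with the linear calculation; the size depends on the assumed rates.

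**The case against.** The other side has a good case.

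- **The SAP keeps its promise.** It undertakes only to summarize the low dose in order to explore dose response. It does that, and adds a low-dose GEE. A reader might infer that it contradicts itself or that the primary result is compromised. Neither follows: within-group crossover comparisons are valid, and the trial is sized for high dose versus placebo only. This stands.
- **The unused data are not most of the control information.** A reader might infer that leaving out 240 placebo attacks weakens the low-dose test several-fold. It does not. Each low-dose child already supplies a matched placebo attack, and the others add between-child information only. The largest linear-scale cut, 24%, needs zero correlation. This stands.
- **The dose difference is not beyond reach.** The two groups contain different children, so anyone can subtract the two planned log odds ratios. That stands too, but the SAP does not plan it, and the result has the larger SE of 0.0791.
- **Power stays poor.** The 0.11 used for the low dose is the high-dose design effect, so it presumes no dose response. At half of it (0.055, an illustration), power is Φ(0.055/0.0722 − 1.96) = 12% separately and 13% to 17% jointly. If the low dose did nothing and the high dose had 0.11, the joint high-versus-low contrast would have Φ(0.11/0.0685 − 1.96) = 36% to Φ(0.11/0.0559 − 1.96) = 50% power. The gain is a narrower interval, not a decisive test.
- **Misreading is conjecture.** A reader might infer that a non-significant low-dose result will be reported as proof of no effect. No section of the SAP plans that inference.

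What these points leave untouched is that an exploratory aim calls for an estimate of the dose difference with an interval, and none is planned although the design supports one.

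**Conclusion.** The point holds as a cheap improvement to an inefficient secondary analysis. The SAP plans no high-versus-low estimate, and its low-dose model uses less of the placebo information than the design allows.

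On the linear scale, a joint model would narrow the low-versus-placebo interval by 11% to 24%, and the high-minus-low interval by 13% (0.0685/0.0791 = 0.87) to 29% (0.0559/0.0791 = 0.71) relative to subtracting the separate estimates. These sizes rest on reading 0.5 as the SD of the within-child difference, on ρ between 0 and 0.5, and on the planned group sizes.

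Even then, the dose difference detectable with 80% power (about 0.16 to 0.19) exceeds the whole design effect of 0.11. The improvement is an honest interval for the dose difference, not a confirmatory answer.

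**What to change.** Leave the high-dose primary GEE exactly as it is. Add to section 5.3 one exploratory GEE on the whole full analysis set, with treatment at three levels (placebo, low, high), period, the SAP's two-level sequence, weight group and predose severity. Report low versus placebo and high versus low as odds ratios with 95% CIs, presented as estimates and not as tests.

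The cost is one extra model on data already collected, with these conditions to state beside it:
- Sequence must stay at two levels. A sequence-by-dose term would remove nearly all of the gain.
- The model assumes a common placebo response across the randomized dose groups, given weight group, and no dose-specific carryover into period-2 placebo.
- High versus low averages two milligram contrasts over the weight strata (1 vs 2.5 mg below 50 kg, 2.5 vs 5 mg at 50 kg and above). The label should say so, because 2.5 mg is the high level in one stratum and the low level in the other.

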## **2. GENERAL CONSIDERATIONS FOR DATA ANALYSIS**

Part 1 and 2 of the study will be analyzed separately. Separate sets of tables, listings and figures will be prepared for Part 1 and Part 2.

After all subjects have completed the double-blind phase of the study (Part I) or prematurely discontinued from the study, all data in Part I will be cleaned, the database will be frozen (soft lock), the study will be unblinded, and an analysis of Part I (double-blind) data will be performed. This will be the primary analysis of the study and a type I error rate (5%) will be allocated for this analysis.

All statistical tests will be 2-sided and performed at the 5% significance level, without multiplicity adjustment.

Likewise, after all subjects have completed Part II (OLE) of the study or prematurely discontinued from the study, all outstanding data queries have been resolved or adjudicated as unresolvable, and the data have been cleaned and finalized, the final analysis of the data will be performed. This final analysis will mainly focus on the OLE.

Analysis results will be presented using descriptive statistics. For categorical variables, the number and percentage of subjects in each category will be presented; for continuous variables, descriptive statistics (the number of subjects [n], mean, standard deviation [SD], median, minimum, and maximum) will be presented.

### **2.1. Analysis Sets**

Analysis sets define the subjects to be included in an analysis. Analysis sets and their definitions are provided in this section. The analysis set will be identified and included as a subtitle of each table, listing, and figure.

#### **2.1.1. Safety Analysis Set**

The safety analysis set includes all enrolled subjects treated study drug (including placebo run-in). For each treatment period (run-in, period 1, period 2, open-label), subjects will be classified according to the treatment actually treated and by dose level (high dose and low dose according to the weight group):

- Placebo (run-in)
- ZNS 1 mg
- ZNS 2.5 mg for the low weight group
- ZNS 2.5 mg for the high weight group
- ZNS 2.5 mg combined
- ZNS 5 mg
- Placebo (double-blind)
- ZNS (open-label)

All safety analyses will be performed using the safety analysis set.

### **2.1.2. Full Analysis Set**

The full analysis set (FAS) includes all subjects who were randomized and administered at least one dose of post randomization study drug. The analysis of all efficacy variables will be performed using the FAS and will be analyzed separately for high dose and low dose groups.

### **2.1.3. Double-Blind Completers Analysis Set**

The completers analysis set includes all subjects treated with study drug during both periods (periods 1 and 2) and who complete the assessment of predose and 2-hour headache pain intensity ratings during each period.

### **2.1.4. Open-Label Extension (OLE) Analysis Set**

The OLE analysis set includes all subjects who completed the double-blind phase, were dispensed and used at least one dose of open-label drug. Subjects who complete the OLE will also be identified.

## **2.2. Treatment Groups**

Generally in analysis of Part 1 data will be summarized by weight group (<50 kg and ≥50 kg) and whenever applicable by dose (<50 kg low dose (1 mg), <50 kg high dose (2.5 mg), ≥50 kg low dose (2.5 mg), ≥50 kg high dose (5 mg) and Placebo). All subjects taking 2.5 mg dose (<50 kg high dose and ≥50 kg low dose together) will also be summarized whenever applicable. For summaries based on the Safety Analysis Set the group of subjects who were not randomized will also be presented.

In analysis of Part 2 data will be summarized by weight group and dose. Subjects in the <50 kg group will receive 2.5 mg dose, and subjects in ≥50 kg group will initially receive 5 mg dose, but may down-titrate to 2.5 mg dose. All subjects receiving 2.5 mg dose and all subjects in the ≥50 kg weight group will also be summarized. Since subjects may have different weight and receive different doses at different time points in the study, the assignment of subjects to treatment groups in Part 2 is not static. The following strategy will be used:

- For treatment-emergent adverse events: each TEAE will be assigned to the dose and its associated weight group based on AE onset date; see section 6.1.6 for details.
- For disposition: subject disposition will be summarized based on the last dose and its associated weight group in the study
- For baseline characteristics and findings: subjects will be summarized based on the first OLE dose that is dispensed to them at Visit 4.
- For findings collected at post-baseline visits: finding will be summarized based on the last dose and its associated weight group that the subject received prior to the visit. If the subject did not treat a migraine headache in Part 2 prior to the visit, the findings will be associated with the last dose dispensed to the subject at a prior visit. For Part 2 baseline the classification will be based on the dose dispensed at Visit 4.

[figure not shown]
- For concomitant medications: each concomitant medication will be associated with the study drug dose and its associated weight group that the subject took prior to the start of the concomitant medication and also with each study drug dose the subject took while taking this concomitant medication.

Details of specific treatment groups for each table are presented in the table shells document.

